10.4.3 Safety Analysis

Safety will be assessed through the analysis of the reported incidence of treatment-emergent AEs. Treatment-emergent AEs are those with an onset on or after the initiation of therapy, and will be graded according to NCI CTCAE v4.0.

The AEs will be coded using Medical Dictionary for Regulatory Activities, and summarized using system organ class and preferred term by dose level for all patients in the Safety Population. In addition, summaries of serious AEs (SAEs), AEs leading to treatment discontinuation, AEs by maximum NCI CTCAE grade, and AEs related to study treatment will also be presented by dose level.

Safety of MLN9708 when used in this indication (primary endpoint) will be evaluated as follows: Toxicity profile data will include AEs, laboratory parameters, vital signs, and other protocol-specified tests that are deemed critical to the safety evaluation. Safety data will be tabulated for all patients who receive any amount of study medication. Adverse events will be tabulated by system organ class, preferred term, severity, and relation to treatment. The tabulation of laboratory parameters will indicate the normal range of each parameter. Each analyte value will be classified as falling above, below, or within the normal range.

Incidence of GVHD (safety secondary endpoint) will be reported in a manner consistent with the AE reporting previously described.

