3. STUDY PATIENT POPULATION AND DISCONTINUATION

3.1 Inclusion Criteria

Patients must meet the following criteria in order to be included in the research study:

1. Symptomatic multiple myeloma or asymptomatic myeloma with myeloma-related organ damage diagnosed according to standard criteria in patients who received allogeneic transplant due to high-risk prognostic features, such as, but not limited to:
 - Chromosome 17p, partial deletion (del(17p), t(4;14), t(14;16), t(14;20)
 - Plasma cell leukemia
 - Progression-free survival of less than 2 years after autologous stem cell transplant

CONFIDENTIAL

STUDY DRUG: MLN9708
FINAL PROTOCOL: 11 APRIL 2014
AMENDMENT NUMBER 3: 11 FEBRUARY 2016

SCRI INNOVATIONS STUDY NUMBER: MM 42

VERSION 4

2. Evidence of engraftment of neutrophils (absolute neutrophil count [ANC] >1000 cells/mm³) and platelets (platelets >60,000 cells/mm³ [dose escalation phase] and >50,000 cells/mm³ [dose expansion phase])
3. Achievement of at least a PR prior to allogeneic stem cell transplant.
4. Adequate liver function defined as:
 - Alanine aminotransferase (ALT) and aspartate aminotransferase (AST) ≤3.0 x the upper limit of normal (ULN)
 - Total bilirubin ≤2.0 x ULN
5. Adequate renal function defined as creatinine clearance ≥30 mL/min, estimated or calculated.
6. Aged ≥18 and ≤70 years, at time of enrollment
7. Ability to swallow oral medication
8. Absence of gastrointestinal symptoms that precludes oral intake and absorption of MLN9708 (nausea, vomiting, diarrhea, malabsorption)
9. Off antibiotics and amphotericin B formulations, voriconazole or other anti-fungal therapy for the treatment of proven, probable or possible infections (defined in accordance with the European Organization for Research and Treatment of Cancer/Invasive Fungal Infections Cooperative Group and the National Institute of Allergy and Infectious Diseases Mycoses Study Group [EORTC/MSG] criteria)
10. Eastern Cooperative Oncology Group (ECOG) Performance Status score of ≤ 2 (Appendix A)
11. Life expectancy ≥3 months
12. Male patients with female partners of childbearing potential and female patients of childbearing potential are required to use two forms of **acceptable** contraception, including one barrier method, during their participation in the study and for 90 days following last dose of study drug. Male patients must also refrain from donating sperm during their participation in the study (Appendix C).

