5.1.3 Maximum-Tolerated Dose

The MTD is the highest dose at which ≤ 1 of 6 patients experience a DLT during 1 cycle (28 days) of therapy. If 2 or more patients in a dosing group of ≤ 6 patients experience a DLT, the MTD has been exceeded. If 2 or more patients in a doses group of up to 6 patients experience a DLT and only 3 patients were evaluated at the previous (i.e., next lower) dose, then an additional 3 patients will be evaluated at this next lower dose and if zero or one have DLTs then this previous dose level is declared the MTD.

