5.1.4 Expansion after Determination of the Maximum-Tolerated Dose

Once the MTD is determined, the MTD cohort of patients will be expanded with an additional 20 patients to further characterize the safety and clinical benefits of maintenance with MLN9708 after allogeneic stem cell transplant. If the MTD is not reached, the expansion will proceed at the MPD.

CONFIDENTIAL

STUDY DRUG: MLN9708
 FINAL PROTOCOL: 11 APRIL 2014
 AMENDMENT NUMBER 3: 11 FEBRUARY 2016

SCRI INNOVATIONS STUDY NUMBER: MM 42

VERSION 4

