10.3 Analysis Population

The following analysis populations will be used:

- The Safety population will consist of all patients who received at least one dose of MLN9708. This population will be used in all safety summaries.
- The Efficacy Evaluable population will consist of all patients with measurable or evaluable disease at baseline who receive at least 1 dose of MLN9708 and undergo at least one post-baseline disease assessment. In addition, patients who discontinued the study prior to their first post-baseline disease assessment due to death or progressive disease will also be included in the Efficacy Evaluable population.

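### Safety at the MTD/MPD is not split by phase, so its column mixes 20 expansion patients with escalation patients selected on few Cycle 1 DLTs; show escalation, expansion and combined columns.

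*Protocol*

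**What the plan says.** Protocol 10.4.3 states that AEs are "summarized using system organ class and preferred term by dose level for all patients in the Safety Population". The summaries of SAEs, AEs leading to discontinuation, AEs by maximum grade and related AEs follow the same layout ("AEs related to study treatment will also be presented by dose level"). The paragraph on the primary safety endpoint adds a tabulation across doses: "Safety data will be tabulated for all patients who receive any amount of study medication". Section 10.3 defines the population for all of these: "The Safety population will consist of all patients who received at least one dose of MLN9708".

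The selected dose is found by rule. Section 5.1.3: "The MTD is the highest dose at which ≤ 1 of 6 patients experience a DLT during 1 cycle (28 days) of therapy". Section 5.1.4 then says "the MTD cohort of patients will be expanded with an additional 20 patients", or that the expansion proceeds at the MPD if no MTD is reached. A column defined by dose level therefore holds both phases.

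Entry criteria differ by phase. Section 3.1 requires "platelets >60,000 cells/mm³ [dose escalation phase] and >50,000 cells/mm³ [dose expansion phase".

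The SAP adds no phase split. Its table list (Tables 4-9 and 14 for treatment and safety) names no columns for these tables, and the subgroup field beside them is empty.

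**The concern.** Safety is a primary objective in both documents, and section 5.1.4 gives further characterisation of safety as a reason for the expansion. The 20 expansion patients are the only group at the selected dose who are not there because of a toxicity rule, yet no specified summary shows them alone. The escalation patients at that dose belong to it because few of them had a DLT, so their Cycle 1 DLT rate is low by construction.

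The effect is not confined to a DLT count. Grade 4 thrombocytopenia and most Grade 3-4 non-hematologic toxicities are DLT criteria (5.1.2), so they feed the Grade 3+ tables. A patient with a Cycle 1 DLT also stops treatment (5.1.2, 6.1), so the selection reaches AEs leading to discontinuation. The direction is known in advance and favours the drug.

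The platelet limits are a separate reason to split. They have nothing to do with selection, but a pooled cytopenia rate averages over two entry populations.

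**Working it through.** **The plan's own figures.** Three cohorts of at most 6 give 3 × 6 = 18, and 18 + 20 = 38. Both match the protocol (10.2 and the synopsis).

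**Inputs.** The MTD rule is at most 1 DLT in 6 during Cycle 1 (5.1.3), with a lower dose filled to 6 if needed. The expansion adds 20 patients (5.1.4). The documents give no DLT rate, so the true Cycle 1 rate p is assumed to lie between 5% and 40% and to be the same in both phases.

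**Selected escalation patients.** With X DLTs in 6 and q = 1 − p, P(X=0) = q⁶ and P(X=1) = 6pq⁵. So E[X | X ≤ 1] = 6pq⁵ / (q⁶ + 6pq⁵) = 6p/(1 + 5p), and the expected rate among the six is p/(1 + 5p).

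**Pooled column.** Expected rate = [20p + 6p/(1 + 5p)] / 26. At p = 0.20 this is (4 + 0.6)/26 = 17.7%.

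**MPD variant.** Table 3 gives no separate action for 0 of 3 at the top dose, so expansion there might follow 0 of 3 or 1 of 6. The weights are q³ (23 patients in the column) and 3pq⁵ (26 patients). At p = 0.20: [0.512 × 4/23 + 0.1966 × 5/26] / 0.7086 = 17.9%.

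| True p | P(X ≤ 1 of 6) | Rate in selected six | Pooled 26 | Bias, points | Bias at MPD variant, points |
|---|---|---|---|---|---|
| 5% | 0.967 | 4.0% | 4.8% | −0.2 | −0.3 |
| 10% | 0.886 | 6.7% | 9.2% | −0.8 | −0.7 |
| 20% | 0.655 | 10.0% | 17.7% | −2.3 | −2.1 |
| 30% | 0.420 | 12.0% | 25.8% | −4.2 | −3.7 |
| 40% | 0.233 | 13.3% | 33.8% | −6.2 | −5.3 |

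**Averaged over which dose is selected.** The full three-level 3+3 with backfill was simulated 400,000 times on each of four assumed curves: (5, 10, 20%), (10, 20, 35%), (15, 30, 45%) and (5, 10, 15%). The mean pooled bias was −1.2 to −2.9 points. Five other assumed curves, with rates from 5% to 50%, gave −1.9 to −3.4.

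**Against sampling error.** At p = 0.20 the column lacks 6 × (0.20 − 0.10) = 0.6 of a patient with a DLT. The standard error from 20 patients is √(0.20 × 0.80/20) = 8.9 points, so the bias is about a quarter of it.

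**Events over all cycles.** Suppose p = 0.20, every DLT counts as a Grade 3+ event, and 40% of patients without a DLT have a Grade 3+ event at some time. The true rate is 0.20 + 0.80 × 0.40 = 52.0%. In the selected six it is 0.10 + 0.90 × 0.40 = 46.0%. Pooled: (20 × 0.52 + 6 × 0.46)/26 = 50.6%, a bias of −1.4 points.

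**Pooled against expansion-only.** For the pooled column, the variance is [20pq + x(1 − x)]/26², where x = 6p/(1 + 5p); adding the squared bias gives the mean square error. At p = 0.20: (3.2 + 0.24)/676 + 0.0231² = 0.0056, whose root is 7.5 points. Expansion-only has 8.9. At p = 0.10 the pair is 5.5 and 6.7, and at p = 0.30 it is 9.1 and 10.2.

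**The case against.** **The affected quantity is narrow.** Selection acts on Cycle 1 DLTs. The listed tables count Grade 3+ AEs, SAEs and frequent AEs over up to six cycles. This stands: the 1-to-4-point figures apply to Cycle 1 DLT-type events, and most tabulated rates move less.

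**Toxicity at the MTD is simply understated.** A reader might infer this, but the shortfall holds only in expectation. In one trial the column can err either way.

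**Safety is summarised only by dose level.** A reader might infer this too. Section 10.4.3 also tabulates all treated patients, and the paragraph on the primary endpoint is the one that says so. The MTD column is therefore not the sole primary safety display, although the all-patient table does not separate phases either.

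**The expansion patients should become the estimate.** It is tempting to prefer the group free of selection. Under the same model the pooled column has the smaller total error, so replacing it trades bias for precision. Showing both is the defensible course.

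**The tables may already have the split.** SAP 1.5 refers to table shells that are not among the documents. What can be said is that a phase split is not specified, not that the final tables will lack one.

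**The column is not exactly six selected patients.** At the MPD it may be three. Dosed patients who were replaced (5.1.2, section 6) stay in the Safety Population. Both change the size of the bias but do not remove the pooling.

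**The platelet limits differ by only 10,000.** True, and their effect cannot be sized from the documents. The difference supports a split but not a claim of material distortion.

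**Conclusion.** The point holds as a minor reporting gap. No phase split is specified, and the column for the selected dose pools 20 expansion patients with a few escalation patients selected on low Cycle 1 toxicity. The expected understatement of the Cycle 1 DLT-type rate is about 1 to 4 points for assumed true rates of 10% to 30%. The larger 6-point figure needs a true rate of 40%, at which six patients would pass the rule only 23% of the time. The sizes rest on assumed DLT rates, six evaluable escalation patients at the selected dose (three or six in the MPD variant), and an equal DLT rate in both phases. The different platelet limits are an independent, unquantified reason to separate the phases. Sample size and MTD determination are unaffected.

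**What to change.** In protocol 10.4.3 and SAP Tables 4-9 and 14, show three columns for the MTD/MPD dose: escalation, expansion and combined. Give exact 95% confidence intervals for key Grade 3+ events in the expansion and combined columns. Add a footnote that the escalation patients at this dose were selected on Cycle 1 DLTs. Keep the combined estimate rather than replacing it with the expansion-only figure.

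The cost is two extra columns per table, with no new data and no change to the design. The expansion column will have a wider interval: 5/20 gives 9% to 49%, against 9% to 44% for 6/26.

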11.1.2 Adverse Events

Adverse event means any untoward medical occurrence associated with the use of a drug in humans, whether or not considered drug related. An AE (also known as adverse experience) can be any unfavorable and unintended sign (e.g., an abnormal laboratory finding), symptom, or disease temporarily associated with the use of a drug, without any judgement about causality. This includes any newly occurring event, or a previous condition that has increased in severity or frequency since the administration of study drug. An AE can arise with any use of the drug (e.g., off-label use, use in combination with another drug) and with any route of administration, formulation, dose or including overdose.

An abnormal laboratory value will not be assessed as an AE unless that value leads to discontinuation or delay in treatment, dose modification, therapeutic intervention, or is considered by the investigator to be a clinically significant change from baseline.

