Adverse Events	Definition of Treatment-Emergent Adverse Event (TEAE): Treatment-emergent AEs are those with an onset on or after the initiation of therapy, and will be graded according to NCI CTCAE v4.0.		
Laboratory Data	Data will be summarized by:  NCI-CTCAE for CTCAE-gradable parameters, and H/L for non-CTCAE-Gradable parameter  H/L for all lab parameters		

Tier 1 Study – Tables, Figures & Listings

Standard TFLs			
Table No	Description	Variables/Analyses To Be Included	Subgroup Analyses
Table 1	Summary of Patient Disposition	 Number of patients screened  Number of patients randomized  Number of patients treated  Reason for treatment discontinuation  Reason for study withdrawals  Other, specify: Patient Deaths; Time on Study	
Table 2	Summary of Demographic Characteristics	 Age: Mean, SD, Median, Min, Max  Age Group:  Sex  Race  ECOG  Other, specify:	
Table 3	Summary of Disease History	 Histology  Disease Staging  Time from Diagnosis  Other, specify: Baseline FISH Baseline Cytogenetics	
Table 4	Summary of Patient Treatment and Dose Modifications (reductions, interruptions)		
Table 5	Summary of Grade 3+ Adverse Events		
Table 6	Summary of Treatment-Related Grade 3+ Adverse Events		
Table 7	Summary of Serious Adverse Events		
Table 8	Summary of Treatment-Related Serious Adverse Events		
Table 9	Summary of Treatment Related Adverse Events Leading to Death		
Table 10	Summary of Best Overall Response		
Table 11	Summary of Response Over Time		
Table 12	Summary of Progression-Free Survival (Kaplan-Meier estimates & 95 CI)		
Table 13	Summary of Overall Survival (Kaplan-Meier estimates & 95 CI)		
Table 14	Summary of Adverse Events with \geq 5% Frequency (for: CTGOV)		

Figure No	Description	Variables/Analyses To Be Included	Subgroup Analyses

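### The planned laboratory tabulation has no CTCAE grade and no baseline comparison, so it cannot show further worsening in patients who enter with low counts or raised liver tests

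*Protocol*

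**What the plan says.** **Laboratory method.** Protocol 10.4.3 includes laboratory parameters in the safety primary endpoint. It says their tabulation will show normal ranges, and then: "Each analyte value will be classified as falling above, below, or within the normal range". It mentions no toxicity grade, worst value or baseline for laboratory data.

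**SAP.** Section 7 Safety, Laboratory Data row, offers two choices. One is "NCI-CTCAE for CTCAE-gradable parameters, and H/L for non-CTCAE-Gradable parameter"; the other is high/low for every parameter. Neither is ticked. Tables 1-14 contain no laboratory table.

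**Entry criteria (Protocol 3.1).** ANC must exceed 1,000/mm³. The platelet rule is "platelets >60,000 cells/mm³ [dose escalation phase] and >50,000 cells/mm³ [dose expansion phase". The liver rule is "Alanine aminotransferase (ALT) and aspartate aminotransferase (AST) ≤3.0 x the upper limit of normal (ULN", with total bilirubin up to 2 x ULN.

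**Adverse events.** AEs are CTCAE graded. Section 10.4.3 adds "AEs by maximum NCI CTCAE grade, and AEs related to study treatment will also be presented by dose level". For laboratory values, section 11.1.2 states: "An abnormal laboratory value will not be assessed as an AE unless that value leads to discontinuation or delay in treatment, dose modification". The sentence goes on to include therapeutic intervention and a change from baseline that the investigator considers clinically significant.

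**Continuous data.** Protocol 10.4 promises mean, median, SD and range for all continuous measures.

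**The concern.** A three-way classification can register worsening only when a value crosses a normal limit. These patients are 45 to 120 days past an allogeneic transplant, and the entry criteria accept values already beyond that limit. For such a patient the category at entry is also the worst category available on that side of normal.

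Safety is a primary objective, and thrombocytopenia is one of the listed drug reactions (section 6.3; 33% in pooled oral studies, section 1.2.5). In a study with no control arm, comparison with the patient's own baseline is the natural way to separate existing post-transplant abnormality from worsening on drug, and to compare dose levels. The protocol uses baseline elsewhere: the DLT rule for patients entering with raised liver tests is relative to baseline (5.1.2), and the immune-cell analyses use change from baseline (10.4.2). The laboratory tabulation in the primary endpoint does not.

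**Working it through.** There is no plan figure to reproduce. The check passes example values through the protocol's own rules.

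**Inputs from the protocol**
- Entry floors (3.1): ANC above 1,000/mm³ = 1.0 x 10⁹/L; platelets above 50,000 or 60,000/mm³ = 50 or 60 x 10⁹/L; ALT/AST up to 3 x ULN.
- Day 8 and 15 holds (Table 4): ANC <0.5 x 10⁹/L or febrile neutropenia; platelets <30 x 10⁹/L.
- Criteria to start the next cycle (6.1.1): ANC at least 1,000/mm³ and platelets at least 40,000/mm³; otherwise delay.

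**Assumed inputs.** Site normal ranges are not in the documents. Lower limits tried: ANC 1.5, 1.8 and 2.0 x 10⁹/L; platelets 130, 140 and 150 x 10⁹/L.

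**Rule.** A value is below if it is under the lower limit, above if it exceeds ULN, and otherwise within.

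**Result** (the same at every assumed limit)

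| Analyte | Entry | Later value | Category, entry to later | Table 4 hold on Day 8/15? |
|---|---|---|---|---|
| ANC (x 10⁹/L) | 1.1 | 0.9 | below to below | no |
| ANC | 1.1 | 0.6 | below to below | no |
| ANC | 1.1 | 0.4 | below to below | yes |
| Platelets (x 10⁹/L) | 51 | 45 | below to below | no |
| Platelets | 51 | 31 | below to below | no |
| Platelets | 51 | 29 | below to below | yes |
| Platelets | 51 | 20 | below to below | yes |
| ALT (x ULN) | 2.9 | 6 | above to above | not covered by Table 4 |
| ALT | 2.9 | 21 | above to above | not covered by Table 4 |

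Every row is unchanged in the laboratory tabulation.

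**Which of these the AE tables recover**
1. ANC 0.4, or platelets 29 or 20, on a dosing day force a hold. Under 11.1.2 that makes them AEs, and they enter the maximum-grade summary.
2. Platelets of 31 still present at the next Day 1 fail the 40 x 10⁹/L criterion, force a delay and so become an AE. ANC still below 1.0 at that visit does the same.
3. ANC 0.6 or 0.9, or platelets 31 or 45, on Day 8 or 15 force no hold. If counts meet the Day 1 criteria by the next cycle, there is no delay either. The value is then an AE only if something else happens: an intervention, extra testing, accompanying symptoms, or an investigator's judgement (11.1.2, 11.1.7, 11.3.3, 11.4.1).

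**Grade of the missed ANC range.** Table 4 labels ANC <0.5 as Grade 4 and recovery to at least 1.0 as Grade 2 or better. ANC from 0.5 to below 1.0 is therefore Grade 3 by the protocol's own labels. A Grade 3 value can thus be absent from SAP Table 5 (Grade 3+ AEs) while the laboratory tabulation shows no change. The documents do not give the full CTCAE platelet and ALT cut-offs, so no grade is assigned to those rows.

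**The case against.** The strongest reply is that the laboratory tabulation is a small part of the safety analysis. Section 10.4.3 opens with treatment-emergent AEs, and further on says "Adverse events will be tabulated by system organ class, preferred term, severity, and relation to treatment". Several routes bring laboratory worsening into those tables:
- the hold and delay rules;
- the clinically-significant-change limb of 11.1.2;
- the rule in 11.3.6 that a worsened pre-existing condition is an AE;
- the rule in 11.4.1 on clinically relevant laboratory deterioration.

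This stands for severe events, and it rules out the stronger reading that the primary endpoint as a whole would show no change at Grade 4. A platelet fall from 55,000 to 10,000/mm³ found on a dosing day forces a hold and becomes a graded AE. An ALT rise from 2.9 to 15 x ULN is 15/2.9 = 5.2 times baseline and falls under the baseline-relative DLT rule in Cycle 1, if judged at least possibly related.

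Two other inferences also fail. Patients starting outside normal are not fixed in one category: values that recover move to within, and only a worse category is closed to them. Nor do the documents present liver toxicity as a main expected effect. Section 6.3 does not list it, Table 2 has no hepatic term, and it is not among the DLTs reported in section 1.2.6. It is a DLT criterion here, and no more should be claimed.

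The continuous summaries in 10.4 are a partial answer. They describe groups rather than individual shifts, no laboratory change from baseline is named, and no SAP table carries them out.

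It is also fair that unticked boxes may mean an unfinished form. Both Per Protocol boxes are blank, and Table 3 has text beside an unticked entry. The point is only that no laboratory method is selected, not that grading was rejected. Nothing is claimed about the listings, which are cut off in the copy read.

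**Conclusion.** The concern holds in limited form. The only laboratory-specific tabulation cannot show patients who enter outside normal moving to a worse category, and the SAP does not fill the gap. What goes unseen is worsening that triggers no action, most clearly ANC 0.5 to below 1.0 x 10⁹/L, or platelets 30,000-50,000/mm³, on Day 8 or 15 with recovery to the next Day 1 criteria. Its capture depends on intervention or investigator judgement, which may differ across up to five sites.

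The number of patients affected cannot be derived, because baseline distributions are not given; the ceiling is the planned 18 + 20 = 38. Dose escalation is unaffected, since it rests on DLTs and not on this table. This is a weakness in describing safety, not a threat to the MTD. The conclusion assumes lower limits of about 130-150 x 10⁹/L for platelets and 1.5-2.0 x 10⁹/L for ANC, and is the same across both ranges.

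**What to change.** 1. In the SAP's Laboratory Data row, tick the existing CTCAE option.
2. Add one laboratory table to the SAP. For each gradable analyte and dose level, give the worst post-baseline CTCAE v4.0 grade and the shift from baseline grade to worst grade. State which value is baseline when both the baseline visit and Cycle 1 Day 1 have been sampled.
3. Add one sentence to Protocol 10.4.3 to match, keeping above/below/within only for analytes without a CTCAE grade.

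The cost is a tick, a sentence and a standard shift table. CBC is already scheduled on Days 1, 8 and 15 of every cycle, and the chemistry panel on Day 1 of every cycle and Days 8 and 15 of Cycle 1 (Appendix D). No visit, sample or treatment rule changes.
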